8.2 Sample size determination

If applicable, provide a justification of the sample size outlined in section 8.1 – to include reflections on, or calculations of, the power of the study.

The proposed study is focused on examining the efficacy, acceptability, feasibility, and the experience of the patient when using virtual reality in treating job interview phobia. The number of participants (300 per intervention condition; 300 General Social Skills Training; 300 Job Interview Phobia; 150 Waitlist Control) was based on Kampmann et al. (2016) who conducted a virtual reality study with adults with social phobia and used similar primary outcome measures. In their study, their power calculations estimated that 300 participants/per intervention group would be sufficient to find significant differences (two sided-power, power= 80%, alpha -0.05, G*Power 3.2) based on an effect size of exposure therapy found in a meta-analysis (Powers et al., 2008).

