1.0 Objectives

22.1 Study Objectives

Describe the purpose, specific aims or objectives. State the hypotheses to be tested.

The purpose of this study is to test the efficacy of virtual reality videos to facilitate exposure therapy in social anxiety disorder (SAD). The exposure therapy videos are the focus of this experiment. Essentially, we are testing the efficacy of the Virtual Reality Exposure Therapy (VRET) scripts (i.e., virtual scenarios, people, and interactions that we expose socially anxious people to). To this end, the goal of the current study is to help people with social anxiety overcome their phobias. Individuals who experience a difficult time building social relationships, accomplishing everyday tasks, or pursuing interviews can practice those same behaviors in a controlled environment.

The study hypotheses are as follows:

1. Virtual reality exposure therapy intervention (vs. waitlist control condition) is effective for treating SAD symptoms.
2. Participants who received the virtual reality exposure therapy will experience maintenance of treatment gains following 3-month and 6-month post-termination of treatment.
3. Users of the virtual reality exposure therapy will demonstrate high amounts of acceptability of the treatment.

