22.2 Primary Study Endpoints

State the primary endpoints to be measured in the study. Clinical trials typically have a primary objective or endpoint. Additional objectives and endpoints are secondary. The endpoints (or outcomes), determined for each study subject, are the quantitative measurements required by the objectives. Measuring the selected endpoints is the goal of a trial (examples: response rate and survival).

To answer these questions, the proposed study will use both qualitative and quantitative methods. Qualitative methods will include a semi-structured interview at the end of the study to gather information on the participant's experience, as well as data collected throughout the therapy process. Quantitatively, the study proposes to use basic descriptive statistics to examine treatment outcomes and engagement with digital tools.

This exploratory study will answer the following questions:

- 1) Compared to the waitlist control condition, is the virtual reality exposure intervention more effective for treating symptoms of social anxiety disorder?
- 2) Are there higher treatment gains maintained over time among participants who receive the virtual reality exposure therapy compared to the waitlist control condition?

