After self-report questionnaires are completed, participants will then complete the baseline clinical interview (paper version of “LIMBIX - Measure - MINI Neuropsychiatric Interview.pdf”) conducted by a study team member who is not the ultimate research therapist. The clinical interview will generally take about 15 to 25 minutes. This interview will be videotaped to conduct reliability assessment on the diagnoses.

Participants who meet the study eligibility criteria will next be contacted by phone by another study team member within a week to receive their random assignment to either the virtual reality exposure therapy condition or the waitlist control condition and to schedule their treatment planning session. Participants in the immediate treatment group will be invited to start treatment soon after the baseline assessments, whereas those in the waitlist control condition will be invited to start this treatment 8 weeks later. The script “LIMBIX - Scripts - Study Therapist to Subject” will be used to facilitate this process.

Within a day the intake assessor completes the initial assessment for an eligible participant, the coordinator will (1) randomly assign the eligible participant who had just completed the interview to their treatment condition, (2) call the participant to inform them of their study condition, and (3) inform their research therapist assigned to be in charge with conducting the 8 to 10 50-minute weekly treatment planning and therapy sessions.

As participants assigned to the treatment condition will begin therapy immediately, the coordinator will communicate this message to the research therapist within a day of the initial assessment.

On the other hand, participants assigned to the waitlist control condition will begin therapy 8 weeks later, and the coordinator will communicate this message within a few weeks after the initial assessment visit.

Once the research therapist receives the message from the coordinator to start scheduling treatment with a particular participant, he or she is expected to contact the participant and set up an appointment within the next one or two weeks depending on their availability.

Step 3: Treatment Planning

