8.0 Participant Numbers and Statistical Plan

8.1 Number of Participants

Indicate the total number of participants to be accrued.

If applicable, distinguish between the number of participants who are expected to be enrolled and screened, and the number of participants needed to complete the research procedures (i.e., numbers of participants excluding screen failures.)

750 participants

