8.3 Statistical methods

Describe the statistical methods (or non-statistical methods of analysis) that will be employed.

We will conduct a series of growth curve analyses to test for treatment efficacy. We will use the R packages 'lme4' (Bates, Maechler, & Bolker, 2012), 'lmerTest' (Kuznetsova & Brockhoff, 2014), and 'lavaan' (Rosseel, 2012) to calculate the growth trajectories for each participants. We will test for the impact of time using participants' scores at post-treatment, and at 6-month and 12-month follow-ups. We intend to perform separate models for each of the study outcome measures.

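### The 300/300/150 split makes the waitlist, the comparator for Hypothesis 1, the smallest arm without explanation; the same 750 people split evenly would estimate that contrast more precisely, and the stated 80% power does not apply against 150

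*Combined protocol and SAP*

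**What the plan says.** Section 8.1 plans "750 participants". Section 8.2 divides them as "300 per intervention condition; 300 General Social Skills Training; 300 Job Interview Phobia; 150 Waitlist Control", a 2:2:1 split. It supports 300 per intervention group by reference to a cited virtual reality trial, with the settings "two sided-power, power= 80%, alpha -0.05, G*Power 3.2" (read here as two-sided alpha 0.05), "based on an effect size of exposure therapy found in a meta-analysis". It prints no effect size, no power for a contrast with 150, and no reason for the ratio.

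Hypothesis 1 in section 22.1 is "Virtual reality exposure therapy intervention (vs. waitlist control condition) is effective for treating SAD symptoms". The first primary question in section 22.2 asks: "Compared to the waitlist control condition, is the virtual reality exposure intervention more effective for treating symptoms of social anxiety disorder". Nothing in sections 22.1 to 22.3 compares the general social module with the job interview module.

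Section 7.2 states that "participants assigned to the waitlist control condition will begin therapy 8 weeks later". It describes assignment to VRET or waitlist, with the module settled afterwards by interest and fit. Section 22.4.3 instead randomises to three groups, and states no ratio.

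**The concern.** The main hypothesis is a contrast with the waitlist, and a contrast is limited by its smaller side. A small control arm is usually chosen so that more people receive treatment. That reason is weaker here, because waitlisted participants are offered the same therapy 8 weeks later: a larger waitlist delays treatment rather than withholding it. Nor can the split be meant to serve a module-versus-module question, since none is posed.

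At stake are the precision of the controlled test of Hypothesis 1 and the accuracy of the power claim. A reader of section 8.2 would take 80% power as applying to the trial's main comparison, but the statement concerns groups of 300 and the comparator has 150.

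**Working it through.** **Inputs.** Group sizes 300, 300 and 150 (section 8.2); total 300 + 300 + 150 = 750, which agrees with section 8.1. Two-sided alpha 0.05 and power 80% (section 8.2). The SD is not given. It is assumed equal in all arms, so it cancels from every ratio below. The documents do not say whether the modules are pooled or compared singly with waitlist, so both are shown.

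**The plan's own figure.** The 300 per group cannot be reproduced without an effect size. Solving backwards, d = (1.960 + 0.842) × √(2/300) = 0.229. This is an assumption implied by the 300, not a value in the protocol.

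**Standard errors in SD units**, SE = √(1/n₁ + 1/n₂):

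| Contrast | 300/300/150 | Even split | Current SE larger by |
|---|---|---|---|
| Pooled VRET v waitlist | 600 v 150: 0.0913 | 500 v 250: 0.0775 | 17.9% |
| Pooled VRET v waitlist | 600 v 150: 0.0913 | 375 v 375: 0.0730 | 25.0% |
| One module v waitlist | 300 v 150: 0.1000 | 250 v 250: 0.0894 | 11.8% |

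**Against the plan's own benchmark of 300 per group**, which needs no effect size. The equal-group equivalent is 2/(1/n₁ + 1/n₂):

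- 300 v 150: 200 per group
- 600 v 150: 240 per group
- 250 v 250: 250 per group
- 500 v 250: 333 per group
- 375 v 375: 375 per group

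For the pooled contrast, the current split falls short of 300 and either even split exceeds it. For one module, 250/250/250 comes closer but still falls short.

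**Illustrative power**, Φ(d/SE − 1.96), with the lower tail negligible:

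| d (assumed) | 300 v 150 | 250 v 250 | 600 v 150 | 500 v 250 | 375 v 375 |
|---|---|---|---|---|---|
| 0.229 | 62.8% | 72.5% | 70.7% | 84.0% | 87.9% |
| 0.3 | 85.1% | 91.8% | 90.8% | 97.2% | 98.4% |
| 0.5 | >99% | >99% | >99% | >99% | >99% |

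**Sensitivity of the 17.9%.** Equal dropout in all arms leaves it unchanged. Dropout of 20% or 30% in the VRET arms alone gives 16.0% or 14.9%. If therapist clustering inflates the VRET variance (an assumed factor of 1.5 to 2.5, not in the documents), the results are:

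- Factor 1.5: √(1.5/600 + 1/150) = 0.0957 against √(1.5/500 + 1/250) = 0.0837, 14% larger.
- Factor 2.5: √(2.5/600 + 1/150) = 0.1041 against √(2.5/500 + 1/250) = 0.0949, 10% larger.

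**Cost to the module-versus-module contrast.** √(2/300) = 0.0816 rises to √(2/250) = 0.0894, an increase of 9.5%.

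**The case against.** The best defence is that limiting the number of diagnosed people who wait is a legitimate reason for a small control arm. Some may leave during the wait, and section 7.1 allows participants to seek care elsewhere. This stands as a real cost, so it would be wrong to infer that the precision is lost for nothing. But the protocol does not offer this reason, and the waitlist does go on to receive the therapy.

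A reader might also infer that the split weakens every primary comparison, including maintenance of gains. The documents do not support that. Treatment for the waitlist begins at 8 weeks and runs 8 to 10 weekly sessions, so it ends at about week 16 to 18. The immediate group's 3-month follow-up falls at about week 21 to 23. No untreated control remains at 3 or 6 months, and no ratio can add precision there.

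Even the early comparison depends on an outcome at the end of the wait. Section 7.2 describes none, and it excludes the waitlist from between-session measures until treatment starts. This objection is sound: the even split pays off only if that assessment exists.

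Finally, a reader might conclude that the trial is underpowered. The low power figures belong to d = 0.229 alone. At d = 0.3 the current split gives 85% to 91%, and at d = 0.5 it exceeds 99%.

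**Conclusion.** The allocation is inefficient for Hypothesis 1 and the first primary question, and it is unexplained. The loss in standard error is 17.9% (pooled, against 250/250/250), 25.0% (pooled, against 375/375) or 11.8% (one module, against 250/250/250). These are increases from the even split to the current one. Seen the other way, the pooled standard error would fall by 15% or 20%, and those two percentages should not be read as the size of the increase.

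The 80% in section 8.2 does not describe a contrast with 150. That conclusion needs no effect size; the specific power values do. The ratios assume a common SD and similar dropout, and they apply to the controlled period before week 8. They also hold for a growth model with the same visits and variance structure in every arm. This is a worthwhile improvement at no increase in sample size. It does not show that the trial cannot answer its main question.

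**What to change.** Keep 750 and state the ratio in both section 8.2 and section 22.4.3. If randomisation is three-way, as section 22.4.3 has it, allocate 250/250/250. If only VRET versus waitlist is randomised, as section 7.2 has it, allocate 375/375. The two sections must be reconciled first. Specify an outcome assessment for both groups at the end of the wait, since the gain depends on it. If 2:2:1 is kept, give the reason in section 8.2 and restate the power for VRET against 150, pooled or by module as the analysis intends, with the effect size printed.

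If enrolment has started, this needs an amendment: apply the new ratio to the remaining participants and include the allocation period in the model.

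The cost is that 100 more people (250 − 150) or 225 more (375 − 150) wait 8 weeks, and some may leave before treatment. Under 250/250/250 the module-versus-module standard error rises 9.5%, a contrast that no hypothesis uses.

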8.3 Statistical methods

Describe the statistical methods (or non-statistical methods of analysis) that will be employed.

We will conduct a series of growth curve analyses to test for treatment efficacy. We will use the R packages 'lme4' (Bates, Maechler, & Bolker, 2012), 'lmerTest' (Kuznetsova & Brockhoff, 2014), and 'lavaan' (Rosseel, 2012) to calculate the growth trajectories for each participants. We will test for the impact of time using participants' scores at post-treatment, and at 6-month and 12-month follow-ups. We intend to perform separate models for each of the study outcome measures.

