4.0 Recruitment Methods

4.1 Identification of participants

Describe the methods that will be used to identify potential participants or the source of the participants. If not recruiting participants directly (e.g., database query for eligible records or samples) state what will be queried, how and by whom.

StudyFinder: If you intend to use StudyFinder (<http://studyfinder.psu.edu>) for recruitment purposes, please indicate this in section 4.1 along with any other methods for identifying participants. Note that information provided in this protocol should be consistent with information provided on the StudyFinder page in your CATS IRB study.

For Penn State Hershey submissions using Enterprise Information Management (EIM) for recruitment, attach your EIM Design Specification form on the Basic Information page in CATS IRB (<http://irb.psu.edu>). See HRP-103 Investigator Manual, “What is appropriate for study recruitment?” for additional information.

For participants we are planning to recruit from the PSU subject pool, we will identify potential participants by using the Social Phobia Diagnostic Questionnaire (“LIMBIX – Screening – SPDQ”) and the Beck Depression Inventory II (“LIMBIX – Screening – BDI-II”). Subject pool participants who screen positive (i.e., they scored >7.38 (85% specificity, sensitivity 82% (Bianca Lauria-Horner, 2016)) on the

SPDQ) and score above 20 on the BDI-II will be invited to an initial appointment to complete the baseline assessments and clinical interview.

For participants we are planning to recruit from the Penn State Psychological Clinic, we aim to reach out to potential clients with social anxiety disorder through these means: (1) Advertising our study at the adult clinic waiting room (see flyer attached at the Appendix); (2) Clients will contact us if they are interested in participating; (3) Therapists will raise awareness to potential clients about our study by giving them the flyer and letting the client contact us if they are interested in participating. Once a client has expressed interest, we will schedule the initial visit comprising baseline assessments to determine their study eligibility.

We also intend to recruit from StudyFinder and will ensure that the information written in this protocol is consistent with that provided on the StudyFinder page of our CATS IRB.

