4.2 Recruitment process

Describe how, where and when potential participants will be recruited (e.g., approaching or providing information to potential participants for participation in this research study).

Participants will be identified through the current Pennsylvania State University Subject Pool, StudyFinder, and the Penn State Psychological Clinic.

For participants recruited from the subject pool, contact information will be obtained from the subject pool and participants will be contacted through email (refer to “LIMBIX - Subject Pool Email”) and phone (refer to “LIMBIX - Screening Consent – Phone.docx”) to be invited to participate in the study.

For participants recruited from the clinic, we will ask therapists to raise awareness of our study with a brief script (refer to “LIMBIX - Scripts - Therapists to Clients - V1.docx”) that enables potential participants to contact us.

For participants recruited from Study Finder, we will use a distinct email (refer to “LIMBIX - StudyFinder Email”).

Once a participant agrees to participate in this study after we do the pre-screening protocol, we will schedule for the in-person initial assessment session to determine whether or not the participant meets the study eligibility criteria. The participant will receive a hard copy of the informed consent form and will be given every opportunity to ask questions about the study along the way.

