16.2 Feasibility of recruiting the required number of participants

Indicate the number of potential participants to which the study team has access. Indicate the percentage of those potential participants needed for recruitment.

During each semester, approximately 800 students are enrolled in the subject pool who are expected to accumulate up to 6 hours of research credits as a course requirement. We would thus have access to a large numbers of people who are willing and able to partake in the present study. The PSU Psychology Subject Pool is thus an abundant resource for the recruitment of study participants and many previous studies with larger social anxiety disorder samples have been conducted within this participant pool. It is feasible that the desired/required number of participants can be recruited based on previous experience with the subject pool. For the past two semesters of subject pool research over 200 students have met criteria for social anxiety disorder via the Social Phobia Diagnostic Questionnaire.

Further, the Penn State Psychological Clinic is the best place for conducting this study primarily because the data is relatively unique to the clinic. The clinic is a rural outpatient community mental health clinic and will provide information generalizable to an understudied segment of outpatient clients.

Furthermore, the use of structured clinical interviews as part of routine practice as well as the Practice-Research Network (PRN) that has seamlessly been incorporated into the daily operations of the clinic allow the Psychological Clinic to provide both ecologically valid and empirically rigorous data (Castonguay, Locke, & Hayes, 2011). These data will therefore be reliably generalizable to both the research and clinical community, particularly the U.S. community mental health centers.

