22.4.3 Method for Assigning Subject to Treatment Groups

Describe the randomization process and how the associated treatment assignment will be made.

Using a random number generator with the “RAND” function on Microsoft Excel, the participants will be randomly allocated to either one of the two treatment conditions (General Social Skills training or Job Interview training) or waitlist condition.

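### Recruitment source is a plausible prognostic factor that should be known before randomisation, but neither the allocation nor the Section 8.3 models use it, so a modest amount of precision is given up

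*Combined protocol and SAP*

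**What the plan says.** Section 4.2 names three channels: "Participants will be identified through the current Pennsylvania State University Subject Pool, StudyFinder, and the Penn State Psychological Clinic".

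Section 4.1 sets a questionnaire pre-screen for one of them. The anxiety cut reads "Subject pool participants who screen positive (i.e., they scored >7.38" on the SPDQ, and the depression condition follows: "and score above 20 on the BDI-II will be invited to an initial appointment". For the clinic, the step is "Once a client has expressed interest, we will schedule the initial visit comprising baseline assessments to determine their study eligibility", with no SPDQ or BDI-II cut stated. None is stated for StudyFinder. All channels then meet the same MINI-based criteria in Sections 3.1 and 3.2.

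On allocation, Section 22.4.3 says that "the participants will be randomly allocated to either one of the two treatment conditions" or to the waitlist, using the Excel random-number function. It mentions neither strata nor blocks. Section 8.2 plans 300, 300 and 150 participants.

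On analysis, Section 8.3 says "We will conduct a series of growth curve analyses to test for treatment efficacy". It lists software and time points and promises a separate model for each outcome. It names no covariate, recruitment source or subgroup.

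Section 16.2, after describing the clinic, says: "These data will therefore be reliably generalizable to both the research and clinical community". No section sets a target number for each source.

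**The concern.** The pre-screen selects pool members for raised depression scores and does not do so for the others. The common MINI criteria contain no depression threshold, so they do not remove that difference. Section 12.1 itself says that social anxiety and depression often occur together. Clinic participants are approached through therapists, so some may already be in care. Section 7.1 allows care elsewhere during the study, and Section 22.4.6.5 marks prior and concomitant therapy as not applicable. Source may therefore also stand in for concurrent treatment, which nothing else in the plan captures.

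A factor of this kind, fixed before randomisation, is normally used to balance the arms and to explain outcome variance. Here it is planned for neither. At stake is some precision in the VRET-waitlist contrast, and whether the remark about clinics in Section 16.2 will have an estimate behind it.

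**Working it through.** **Inputs from the documents.** Total 750 (Section 8.1). Arms 300:300:150, 80% power, two-sided alpha 0.05 (Section 8.2). The effect size is not given as a number.

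**Assumed inputs.** Within-source SD of 1; pool share p from 50% to 90%; share of outcome variance explained by source (R²) from 1% to 10%. For simplicity the clinic and StudyFinder are taken together as non-pool, and the two VRET modules are pooled (600 v 150). No dropout.

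**The plan's own figure.** Without an effect size, 300 per group can only be solved backward. With 1.960 + 0.842 = 2.802, the detectable effect is d = 2.802 × √(1/n₁ + 1/n₂).
- 300 v 300: 2.802 × 0.0816 = 0.229. As a check, 2 × 2.802² / 0.229² rounds up to 300.
- 300 v 150: 2.802 × 0.1000 = 0.280.
- 600 v 150: 2.802 × 0.0913 = 0.256.

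**What R² could be.** If pool and non-pool outcomes differ by D (in SD), R² = p(1−p)D² / (1 + p(1−p)D²). At p = 0.7:
- D = 0.2: 0.0084/1.0084 = 0.008.
- D = 0.5: 0.0525/1.0525 = 0.050.
- D = 0.8: 0.1344/1.1344 = 0.118.

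**Gain from adjustment.** The standard error is multiplied by √(1−R²). Starting from 80% power at the detectable effect, power becomes Φ(2.802/√(1−R²) − 1.960). The unadjusted sample size with the same precision is 750/(1−R²).

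| R² | Power | Equivalent N |
|---|---|---|
| 0.01 | 80.4% | 758 |
| 0.05 | 82.0% | 789 |
| 0.10 | 84.0% | 833 |

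These figures are for a single-time-point comparison of means.

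**Chance imbalance.** Under unrestricted allocation the 95% range for the difference in pool share is ±1.96 × √(p(1−p)(1/600 + 1/150)). At p = 0.7 this is 1.96 × √(0.21 × 0.00833) = ±0.082. With D = 0.5 it moves the contrast by up to 0.082 × 0.5 = 0.041 SD. The unadjusted 95% half-width is 1.96 × 0.0913 = 0.18 SD.

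**Precision by source.** The non-pool half-width is 1.96 × √(1/n₁ + 1/n₂).
- p = 0.5 (300 v 75): 0.25 SD.
- p = 0.8 (120 v 30): 1.96 × 0.204 = 0.40 SD.
- p = 0.9 (60 v 15): 0.57 SD.

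For a source-by-treatment interaction at 80% power, the detectable difference is 2.802 × √(sum of 1/n over the four cells). It is 0.51, 0.64 and 0.85 SD at p = 0.5, 0.8 and 0.9, against 0.256 SD for the main effect.

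**The case against.** Section 8.3 is brief and does not even write out a treatment term. A reader might infer that the models exclude source, but the text is only silent on it.

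A reader might also infer that the trial enrols differently defined populations. It does not: the pool cuts decide who is invited, and final eligibility is common. No section reports severity or outcome by source, so a prognostic difference is plausible but not shown.

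It is tempting to say that chance imbalance in source distorts the VRET effect. It does not bias it. Under randomisation that imbalance is already part of the standard error, so it is the same loss as the lost precision and must not be counted again.

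Section 16.2 could be read as claiming that the pooled result carries over to clinics. In context, the sentence concerns clinic data and explains why the clinic was chosen for recruitment.

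The size of the gain is also open to challenge. If efficacy is tested as treatment-by-time, stable level differences between sources fall into the person intercept, and a source main effect alone achieves little. A baseline score in the model would absorb part of the difference, although Section 8.3 lists none.

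All of this stands, and it limits the point to efficiency. It does not remove it: a factor selected on differently by channel, and cheap to use, is used neither in the allocation nor in any stated model.

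**Conclusion.** The point holds as a modest efficiency issue. The plan gives up about 0.4 to 4 power points if source explains 1% to 10% of outcome variance. That range is an assumption, the documents do not narrow it, and the figures suit a comparison of levels better than a comparison of slopes. The validity of the randomised comparison is unaffected.

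The remark on generalisability needs a limit. Section 16.2 reports about 800 pool students per semester, and over 200 meeting SPDQ criteria in the past two semesters, with no target per source. The pool could therefore dominate. At an assumed 80% pool share, the clinic and StudyFinder together would supply about 120 VRET and 30 waitlist participants, and the clinic alone fewer. An interaction test would be too weak to settle whether the effect differs by source.

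**What to change.** 1. List recruitment source as a recorded data item. The separate channels suggest that it will be known, but no section says it is recorded.
2. Reconcile Section 7.2, Step 3, where the module follows the participant's interest, with Section 22.4.3, where the module is randomised. The strata and ratio cannot be fixed until these agree.
3. Then allocate in permuted blocks within each source. At the planned 300:300:150 (2:2:1), block sizes are multiples of five. Separate unrestricted lists for each source would not balance the arms; the blocking does that.
4. Include source as a fixed effect in every Section 8.3 model, and source-by-time wherever efficacy is tested as treatment-by-time.
5. Report the VRET-waitlist estimate by source with confidence intervals, labelled descriptive. Limit the Section 16.2 statement to what the clinic participants' own estimate and its precision support.

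The cost is a slightly more complex allocation procedure, a few model terms, and source-specific estimates that readers must be told are imprecise. No visits or participants are added. The blocking has to be in place before enrolment; the model terms should be specified before outcome data are seen.
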